As a palliative care intervention, the AME was developed to help manage distress and offer psychosocial support during acute cancer treatment. Three preliminary Active Music Engagement studies were conducted by our research team. **Study 1** was a descriptive study conducted to measure the presence/absence of contextual support (i.e., structure, autonomy support, relationship support) in the environment and levels of child engagement across three conditions (usual care, AME, and audio-storybooks). Findings indicated that the AME intervention: 1) was theoretically aligned with [name]'s Contextual Support Model for Music Therapy (CSM-MT), and 2) engaged children significantly more than usual care or attention control conditions.

**Study 2** was a multi-site, non-randomized (sequential assignment) study that established feasibility/acceptability of a single-session, therapist-led AME intervention and audio-storybooks as an attention control condition. In this study we examined two attention control conditions (music listening and audio-storybooks). Music listening did not demonstrate any significant behavioral benefits and was not well accepted by parents. In contrast, the audio-storybooks condition was acceptable to parents but did not demonstrate any significant behavioral benefits, validating it as the best control condition for our current study. In addition, children randomized to the AME intervention demonstrated significantly more engagement behaviors than children in the control conditions (i.e., the proximal mediator proposed in this trial).

**Study 3** was a randomized pilot study that examined feasibility, acceptability, and preliminary efficacy of a parent implemented AME. In this study we translated the AME into a parent-led intervention and added parent instruction/coaching. Findings indicated the intervention and design were feasible, highly acceptable, demonstrated significantly more child engagement and parent child interaction behaviors, and produced positive outcomes for children. However, although parents were able to deliver the intervention they expressed: 1) preference for more therapist involvement/support during

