The child/parent also receive a music play resource kit to use during and between therapist-led sessions. The kit includes: 1) a professional CD recording of music composed and/or arranged specifically for this project, 2) age-appropriate musical instruments and play materials that correspond with each activity, and 3) activity cards designed to give children/parents at-a-glance information on ways they can use their kit. Universal precautions and hospital sterilization protocols will be observed for the compact disc players, compact disc recordings, music play resource kits, and other study materials. Children receive their own music play resource kit to keep both during and after study completion.

**Attention Control (Audio-storybooks).** Parents/children randomly assigned to the audio-storybooks attention control condition will have the same length of sessions (45 minutes) and timing of contact (3 sessions, 3 consecutive days) as the AME intervention group. Session 1 is delivered within 24 hours of hospital admission. The audio-storybooks (ASB) condition is designed to control for attention from an intervener, shared parent-child experiences, and audio-visual stimulation. It offers parents/children opportunities to make choices and engage in an age-appropriate, non-music-based play activity. In each session children/parents will choose and listen to one of two illustrated children's books with audio-taped narration. Children/parents receive a kit that includes 3 audio-storybooks that they can keep. Universal precautions and hospital sterilization protocol will be observed for the compact disc players, compact disc recordings, audio-storybooks kit, and other study materials. Children receive their own audio-storybooks kit to keep both during and after study completion.

All study condition sessions will be video recorded to facilitate collection of behavioral outcome data and monitor treatment fidelity. Sessions 1 and 2 are video recorded to desensitize children/parents to video recording; only Session 3 video data are analyzed for Aims 1 and 2. In our previous studies, video recording did not negatively affect participant accrual or cause distress. An evaluator, blind to randomization status, will administer T2 measures after Session 3. Evaluators administer T3 measures 30 days (+/- 7 days) post-intervention during a subsequent clinic visit or by telephone. All evaluation sessions are audio-recorded to monitor evaluation fidelity.

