**Main analyses:** For analyses below we will analyze as randomized and attempt to collect outcome data on non-completers, following the intent-to-treat principle. For Aims 1 and 2, each outcome will be modeled separately. Also we will model T2 separately from T3. Thus, there will be a total of 12 models in Aim 1 (6 outcomes x two time points). In Aim 2, two outcomes will be examined and 3 potential moderators at two time points for a total of 12 (2 outcomes x 3 moderators x 2 time points) models. For Aim 1, our primary goal is to test mediation effects. Mediation effects will be estimated in an ANCOVA setting, fitting the appropriate mediation models using MPlus and then testing indirect effects using the percentile bootstrap approach to estimate the indirect effect. The multiple mediation model with three-path mediation effects specifies that the intervention will act through the proximal and distal mediator on the outcome and also have a direct effect on the outcome. Each outcome model will have 6 key predictors (intervention, two proximal mediators, 3 distal mediators), and control for T1, age (3-5 years vs. 6-8 years), site, and any imbalanced baseline covariates found above (allowing for up to 6 imbalances). Thus we will have up to 15 variables in any model. For Aim 2, we will test moderation effects by including the appropriate interaction terms of the potential moderator (dichotomized at the median) with the intervention indicator (AME vs. attention control) in our models. For all models in Aims 1 and 2, we will assess goodness-of-fit (GOF) using standard GOF measures (comparative fit index, root mean square error of approximation, and root mean square residual). For Aim 3, an exploratory aim, we will use ANCOVA to compare changes in child symptom distress at T2 and T3 between intervention and control groups. In light of positive findings, we next will explore models as in Aims 1 and 2 to assess for potential mediation and moderation effects for this outcome.

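### The Aim 1 mediation models assume, without saying so or checking it, that each mediator has the same slope in both arms, so the indirect/direct split could be wrong in either direction

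*Combined protocol and SAP*

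**What the plan says.** All of this is in the combined protocol and SAP. In Section 7.0 (Main analyses), testing mediation is the primary goal of Aim 1. The model "specifies that the intervention will act through the proximal and distal mediator on the outcome and also have a direct effect on the outcome". Its content is then listed: "Each outcome model will have 6 key predictors (intervention, two proximal mediators, 3 distal mediators"). The models also "control for T1, age (3-5 years vs. 6-8 years), site, and any imbalanced baseline covariates found above (allowing for up to 6 imbalances"), and the total follows: "Thus we will have up to 15 variables in any model". Inference is by "testing indirect effects using the percentile bootstrap approach to estimate the indirect effect".

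Interaction terms appear only under Aim 2, which tests moderation by "including the appropriate interaction terms of the potential moderator (dichotomized at the median) with the intervention indicator". Those moderators are prior distress and child age, not the mediators.

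Section 6.0 lists child engagement and parent-child interaction as the proximal mediators, scored by trained coders at Session 3. Under Section 5.0, Session 3 is therapist-led music play in the AME arm. In the control arm it is an audio-storybook session, in which families "engage in an age-appropriate, non-music-based play activity".

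**The concern.** With one slope per mediator, the model takes a unit of coded engagement to have the same effect on the outcome whether the child is making music or following a narrated book. The same holds for parent-child interaction, and for the links from both to the distal mediators. The plan does not state this assumption, check it, or say which indirect effect is the target if it fails.

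The planned fit indices would not reveal a failure. They compare the covariances of the variables in the model with those it implies, and an omitted product is not among those variables.

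At stake is the trial's main result. The stated objective is to learn through which variables AME works, and the split between indirect and direct effects is how the analysis answers that.

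**Working it through.** **1. Does the listed model leave room for an intervention-by-mediator term?** Key predictors: 1 intervention + 2 proximal + 3 distal = 6. Adjusters: T1 (1) + age (1) + site (counted as 1) + up to 6 imbalances = 9. 6 + 9 = 15, exactly the stated maximum, so no product term is included. (Section 4.0 names four hospitals and the Setting paragraph of Section 5.0 says three. With site as indicator variables the count would be 17 or 16, still without a product.)

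**2. Sample size.** Section 3.0: 184 dyads recruited, 15% attrition. 184 × 0.85 = 156.4, which agrees with the stated 156, or 78 per arm.

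**3. What the common-slope model estimates.** Let *a* be the arm difference in the mediator, b0 and b1 its slopes in control and AME, and s0 and s1 its within-arm SDs. In large samples the common slope is

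b = (s0²·b0 + s1²·b1) / (s0² + s1²),

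the planned indirect effect is *a*·b, and the direct effect is the total minus *a*·b. With separate slopes there are two indirect effects: *a*·b1 at the AME slope and *a*·b0 at the control slope.

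**4. Illustration.** The documents refer to preliminary effect sizes but print none, so every value here is assumed: one mediator, no covariates, *a* = 0.8 SD, no true direct path, control mediator mean 0, s0 = s1. The total is then 0.8 × b1.

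| Slope, control / AME | Total | Planned indirect | Planned direct | Indirect at AME slope | Indirect at control slope |
|---|---|---|---|---|---|
| 0 / 0.4 | 0.32 | 0.8 × 0.20 = 0.16 | 0.16 | 0.32 | 0 |
| 0.1 / 0.4 | 0.32 | 0.8 × 0.25 = 0.20 | 0.12 | 0.32 | 0.08 |
| 0.2 / 0.4 | 0.32 | 0.8 × 0.30 = 0.24 | 0.08 | 0.32 | 0.16 |
| 0.3 / 0.3 | 0.24 | 0.8 × 0.30 = 0.24 | 0 | 0.24 | 0.24 |
| 0.4 / 0.1 | 0.08 | 0.8 × 0.25 = 0.20 | −0.12 | 0.08 | 0.32 |

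Unequal SDs move the result. For slopes 0 / 0.4 with AME SD 1, a control SD of 1.3 gives 0.8 × 0.4 / (1 + 1.69) = 0.119, and a control SD of 0.7 gives 0.8 × 0.4 / (1 + 0.49) = 0.215.

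**5. Precision at 78 per arm.** In 3,000 simulated trials per setting (equal mediator SDs, residual SD 1), the means agreed with the table. The SDs of the indirect estimate were:

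| Slopes, control / AME | Planned | At control slope | At AME slope | Ratios to planned |
|---|---|---|---|---|
| 0 / 0.4 | 0.075 | 0.094 | 0.112 | 1.25, 1.49 |
| 0.1 / 0.4 | 0.077 | 0.092 | 0.115 | 1.19, 1.49 |
| 0.3 / 0.3 | 0.082 | 0.104 | 0.109 | 1.27, 1.33 |

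Intervals are thus about 1.2 to 1.5 times wider. If the mediator SD in AME is half that in control (slopes 0.1 / 0.4), the AME-slope ratio is 0.191 / 0.086 = 2.2.

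**6. Power to see a slope difference.** The SE is about √(2/78) = 0.160. At two-sided 0.05 (assumed), power is 24% for a difference of 0.2, 47% for 0.3, 71% for 0.4 and 80% for 0.45.

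**The case against.** The strongest reply is that different activities do not imply different slopes. Section 6.0 lists the same coding form for the mediators in both arms, and preliminary Study 1 compared engagement across usual care, AME and storybooks. Nothing in the documents gives a mediator-to-outcome slope by arm. This stands, and it is why the point is a risk only.

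A reader might infer more from Section 1.0, where in Study 2 "the audio-storybooks condition was acceptable to parents but did not demonstrate any significant behavioral benefits", and conclude that engagement with storybooks does not lower distress. The text does not support that. The behaviour it goes on to report is engagement itself, which it labels the proximal mediator. Lower engagement in control concerns the path from intervention to mediator, and a common-slope model already allows for it.

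A reader might also infer that the plan will understate mediation and report the rest as direct. That holds only if the AME slope is larger and the effect at the AME slope is the target. At the control slope the planned figure is too high (0.16 against 0 in the first row of the illustration), and with reversed slopes it overstates the effect at the AME slope (0.20 against 0.08).

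Finally, the richer model is not always the more accurate one. With the AME slope at 0.4 and 0.32 as the target, root mean squared errors over 4,000 simulated trials (planned against product-term model) are 0.178 and 0.116 at control slope 0; 0.142 and 0.113 at 0.1; 0.114 and 0.114 at 0.2; 0.095 and 0.113 at 0.3; and 0.093 and 0.115 at 0.4. The planned model is as good or better once the control slope reaches about half the AME slope. This stands, and it argues against replacing the main analysis.

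**Conclusion.** The gap is real: the variable count shows that no intervention-by-mediator term is planned for Aim 1, and the equal-slope assumption is neither stated nor checked. The consequence is conditional. With the AME slope at 0.4 and the control slope between 0 and 0.2, the planned indirect effect lies midway between the two arm-specific values, 0.08 to 0.16 from each. With equal slopes there is no error. The total AME-versus-control effect is unaffected throughout. The sizes rest on assumed slopes, an assumed 0.8 SD difference, equal mediator SDs and a single mediator; the plan has five mediators in a chain, so they are illustrative. This is a cheap improvement to a mechanistic trial, not an error that invalidates the plan.

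**What to change.** Keep the common-slope model as the main analysis and state its equal-slope assumption. Prespecify a sensitivity analysis that adds AME × child engagement and AME × parent-child interaction to the distal-mediator equations, because Hypothesis 1.1 concerns those links, as well as to the outcome equations.

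Report the proximal-mediator slopes by arm, and the indirect effect at the AME slope and at the control slope, with percentile bootstrap intervals, beside the planned result. Do not drop the products because a test is non-significant: at 47% power for a slope difference of 0.3, such a test cannot establish equal slopes. If the indirect effect is not consistent across the analyses, qualify the mechanism conclusion. State beforehand what counts as consistent, in terms of sign and size rather than significance.

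The cost is SAP wording and two more terms per equation, with no new data. The outcome model goes from 15 to 17 variables, or from 156/15 = 10.4 to 156/17 = 9.2 retained dyads per variable. Intervals for the arm-specific effects are about 1.2 to 1.5 times wider when mediator SDs are similar. The distal-mediator slopes stay common; freeing all five would take 20 variables (156/20 = 7.8 dyads per variable), which is harder to justify at this sample size.

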### **Aim 2: Examine moderators of the AME intervention on outcomes for young child and parent distress.**

Hypothesis 2.1: Child and parent distress with prior hospitalizations and child age will moderate intervention effects for child emotional distress and parent emotional/traumatic distress outcomes at Time 2 and Time 3.

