### **3.0. SAMPLE ELIGIBILITY CRITERIA**

**Child/Parent Inclusion Criteria and Rationale:** Children and parents/caregivers will be eligible if: 1) the child is 3 – 8 years of age at time of enrollment (intervention content is not age-appropriate for other children); 2) patients with an expected treatment course of at least 3 days to receive moderate to high intensity chemotherapy and/or radiation therapy either in-patient or outpatient (children receiving chemotherapy are at risk for high symptom distress; 3-day treatment course is required to deliver study conditions and contributes to sample homogeneity); and 3) one parent/caregiver ( $\geq 18$  years of age) can be present for all sessions (study targets both child and parent/caregiver).

**Child/Parent Exclusion Criteria and Rationale:** Children and parents/caregivers will be excluded if: 1) the child and/or parent/caregiver do not speak English or 2) the child has a significant cognitive impairment that might hinder participation (determination made in consultation with attending physician, oncologist, and parents).

**Sample Size.** We will recruit a total sample size of 184 child and parent/caregiver dyads (368 total) and assume 15% attrition in order to retain 156 child and parent/caregiver dyads (78 dyads/group) at Time 3.

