**Data Collection & Randomization Procedures.** Following consent, the project manager will arrange a time for parents/caregivers to complete baseline (T1) measures during a routine clinic visit, prior to their next scheduled chemotherapy admission. A trained evaluator will administer measures in a quiet/private setting and remain available for questions. The child/parent or caregiver dyad will then be stratified by child age (preschoolers 3-5 years; school-agers 6-8 years) and randomized in blocks of six to the AME or attention control condition by our statistician. After the PI or project manager from the enrolling site receives randomization status from our study statistician, she will inform the parent/child of their randomization status and will then immediately schedule Session 1. Only the

project manager, PI, statistician, and intervener will know the child/parent dyad's randomization status. Evaluators will be blinded.

[figure not shown]
All study condition sessions will be video recorded to facilitate collection of child engagement and parent-child interaction data and monitor treatment fidelity. Sessions 1 and 2 are video recorded to desensitize children/parents to video recording; only Session 3 video data are analyzed for Aim 1. In our previous studies, video recording did not negatively affect participant accrual. An evaluator, blind to randomization status, will administer T2 measures after Session 3. Evaluators will administer T3 measures 30 days (+/- 7 days) post-intervention during a subsequent clinic visit or by telephone. Parent self-reports will be used to monitor use of study condition activities between sessions and between T2 and T3 data collections (Appendix 1).

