## 5.0. RESEARCH DESIGN, METHODS, AND PROCEDURES

**Conceptual Framework.** Our conceptual framework (Figure 1) is based on [name]'s Contextual Support Model of Music Therapy and further informed by Kazak's Pediatric Medical Traumatic Stress Model, which provides a useful heuristic for understanding short and long-term consequences of pediatric cancer treatment for parents and their child. In our conceptual framework, recurring events related to cancer treatment (i.e., hospitalizations, procedures) are viewed as potentially traumatic events. Parent appraisal of events as traumatic or not traumatic is influenced by pre-existing factors, which serve as antecedents in our study.

Published research indicates that higher parent and child distress during cancer treatment and survivorship is related to: 1) demographics (younger child/parent age, female parent gender, and lower socio-economic status/education), 2) higher parent/child distress with prior hospitalizations, and greater traumatic stress symptoms, and 3) disease and treatment characteristics (diagnosis, relapsed disease, greater treatment intensity).

Figure 1: Conceptual Framework

The AME directly targets the proximal mediators of child engagement and parent-child interaction, as well as distal mediators of perceived family normalcy, parent confidence (self-efficacy) about their ability to support their child during treatment, and independent music play between therapist-led sessions.

[figure not shown]
Our study examines proximal and distal mediators of the AME on outcomes for young children (emotional distress, physical symptom distress (exploratory), quality of life), parents (emotional distress, traumatic distress, quality of life), and family function. In addition, we examine moderators of the AME intervention on outcomes (child/parent distress with prior hospitalizations; child age). This study will allow us to determine *how* and *for whom* the intervention works, informing a subsequent trial to examine cumulative impact/efficacy of AME across repeated cancer treatment admissions to manage distress and prevent traumatic stress symptoms in survivorship. Findings will also have implications for use of the CSM-MT to guide development of active music interventions to manage treatment distress in other populations.

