## 6.0. MEASURES AND DATA COLLECTION INSTRUMENTS

All measures reflect careful consideration of psychometric properties, sensitivity to change, and response burden. See Appendix 1 for measures and additional psychometrics.

Variable(s)	Measure	# Items	Reliability Evidence	Admin. Schedule	Completed By
Antecedent Factors					
Demographics -parent/child age, parent gender, SES, parent education	Family Information Form	3	N/A	T1	Parent
Prior Distress w/ Hospitalization -parent/child	Prior Illness Experiences Scale (PIES) Abbreviated PTSD checklist (PCL-S)	13 6	.78† .94†	T1 T1, T2, T3	Parent Parent
Disease Characteristics Treatment Characteristics	Diagnosis and Treatment Form Intensity of Treatment Rating Scale Medication Data Form	2 1 7	N/A .95* N/A	T3 T3 T1, T2, T3	Evaluator Oncologist Evaluator
Proximal Mediators					
Child Engagement Parent-Child Interaction	Behavioral Coding Form Behavioral Coding Form	N/A N/A	.85* .85*	Session 3 Session 3	Trained Coder Trained Coder
Distal Mediators					
Family Normalcy Perspective	Family Management Measure (FaMM) Family Life Difficulty Subscale	14	.90†	T1,T2,T3	Parent
Parent Self-Efficacy	Parental Beliefs Scale (PBS)	20	.85†	T1,T2,T3	Parent
Independent Music Play	Parent Report	2	N/A	Sessions 2/3; T2	Parent
Child Outcomes					
Child Emotional Distress	CHQ – Mental Health Subscale	16	.81†	T2, T3	Parent
Child Physical Symptom Distress	Edmonton Symptom Assessment System (ESAS)	3	.69-.80†	T1, T2, T3	Parent
Child Quality of Life	KINDL R	20	.89†	T1, T2, T3	Parent
Parent Outcomes					
Parent Emotional and Traumatic Stress Symptoms	Profile of Mood States-Short Form (POMS) Impact of Events Scale-Revised (IES-R)	37 22	.99** .84-.91†	T1,T2,T3 T1, T2, T3	Parent Parent
Parent Quality of Life	Index of Well-being	9	.93†	T1, T2, T3	Parent
Parent/Child Outcomes					
Family Function	(FACES II)	30	.90†	T1,T2,T3	Parent

†Cronbach's alpha; \*inter-rater reliability; \*\*correlation with POMS

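### Aim 2 prior-distress moderators are tested only as median splits; entering the T1 scores as continuous would be a cheap gain in efficiency if moderation is roughly linear

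*Combined protocol and SAP*

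**What the plan says.** Section 2.0, Aim 2, hypothesises that "Child and parent distress with prior hospitalizations and child age will moderate intervention effects" on child and parent distress at Time 2 and Time 3. Section 7.0 (Main analyses) gives one method, "including the appropriate interaction terms of the potential moderator (dichotomized at the median) with the intervention indicator", and counts "a total of 12 (2 outcomes x 3 moderators x 2 time points) models". It gives no continuous version, no sensitivity analysis and no reason for the split.

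The prior-distress row of the Section 6.0 table lists "Prior Illness Experiences Scale (PIES) Abbreviated PTSD checklist (PCL-S", with 13 and 6 items respectively, both completed by the parent and both scheduled at T1. No section names a cut-off for either score.

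For Aim 3, Section 7.0 says that, after positive findings, "we next will explore models as in Aims 1 and 2 to assess for potential mediation and moderation effects for this outcome", so the split carries over to physical symptom distress.

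Child age already has a defined grouping. Section 4.0 has dyads "stratified by child age (preschoolers 3-5 years; school-agers 6-8 years", and Section 7.0 lists the same two age bands as a model covariate. The Aim 2 text does not say whether the age interaction uses these bands or the sample median.

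**The concern.** A median split treats every dyad on one side of the cut as alike. If the benefit of AME rises or falls gradually with prior distress, the differences within each half carry information about the interaction, and the split discards it. The scores are collected anyway, and the cut depends on who happens to enrol, not on a threshold that the documents justify.

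Aim 2 is where the trial asks for whom AME works. Interaction tests are weak at this sample size even when analysed efficiently, so avoidable loss makes a true moderator easier to miss and a negative result harder to interpret. For age the matter is only clarity: the reader should know which age groups the result refers to.

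**Working it through.** **Inputs.** From Section 3.0: 184 dyads recruited and 15% attrition, to "retain 156 child and parent/caregiver dyads (78 dyads/group) at Time 3". From Section 7.0: the model count and the split. Assumed, because the documents do not give them for Aim 2: two-sided alpha 0.05, the interaction size, the score distribution and the shape of moderation.

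**1. The plan's own figures.** 156 / (1 − 0.15) = 183.5, rounded up to 184, which agrees. Models: 2 outcomes × 3 moderators × 2 times = 12, which agrees. Of these, 2 × 2 × 2 = 8 use a prior-distress moderator and 2 × 1 × 2 = 4 use age.

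**2. Information kept under linear moderation.** This is the squared correlation between the score and its median split. For a normal score it is 2/π = 0.637. On that measure 156 dyads act like 156 × 0.637 ≈ 99, and matching the continuous analysis would need 156 / 0.637 ≈ 245. For other shapes: uniform 0.75, gamma with skewness 1 0.59, exponential 0.48.

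**3. Power by formula.** With 1:1 allocation, residual SD 1 and a standardised score, the interaction SE is 2/√156 = 0.160. At 0.45 outcome SD per moderator SD:
- continuous: 0.45/0.160 = 2.81; Φ(2.81 − 1.96) = 80%;
- split: 2.81 × √0.637 = 2.24; Φ(2.24 − 1.96) = 61%.

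**4. Power by simulation.** 8000 runs per row, N=156, normal score, linear moderation, four sites as covariates. No baseline outcome is included, since Section 6.0 schedules the child measure (CHQ) at T2 and T3 only.

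| Interaction (outcome SD per moderator SD) | Continuous | Split | Formula (continuous / split) |
|---|---|---|---|
| 0 | 4.9% | 4.8% | – |
| 0.30 | 44% | 28% | 47% / 32% |
| 0.45 | 77% | 55% | 80% / 61% |
| 0.60 | 95% | 79% | 96% / 85% |

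A separate simulation at 0.45 gave 78% and 56%. The split falls further below its formula value because score variation within each half goes into the residual. So the formula's detectable effect for the split is slightly optimistic. With 80% power it is (1.960 + 0.842) × 0.160 = 0.449 continuous and 0.449/√0.637 = 0.562 split, but simulated split power at 0.562 is only about 72% to 76%, depending on the assumed main effect of the score.

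**5. Other shapes of moderation.**
- Step at the median, normal score: the split is more powerful, about 79% against 60%. If the step sits at the population median, so that the sample cut misses it slightly, the figures are 72% against 56%.
- Normal score, effect linear between the quartiles and flat outside: squared correlation with the true effect curve is 0.84 continuous and 0.84 split, so there is no gain.
- Exponential score, linear up to the 75th percentile and then flat: 0.67 continuous, 0.80 split, so the split is better.
- Gamma score with skewness 1, same plateau: 0.79 continuous, 0.76 split, so there is almost no gain.

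**The case against.** The strongest reply is that the advantage depends on a shape the documents do not establish. A plateau or step removes or reverses it, and the largest losses calculated for skewed scores are those that lean most on linearity into the tail. This stands, and it is why the median split should be kept as a sensitivity analysis. Section 5.0 does speak of "higher parent/child distress with prior hospitalizations, and greater traumatic stress symptoms", but as correlates of distress; the sentence is not evidence that moderation is graded.

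It is also fair to say that Section 7.0 makes mediation the primary goal of Aim 1, that Aim 3 moderation is exploratory and conditional, and that at 0.30 per SD both tests are weak (44% and 28%). Scoring detail may sit in Appendix 1, which is not shown. These points limit the importance of the change but do not argue against making it.

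A reader might infer that all 12 models are affected, or that the age cut contradicts the randomisation strata. The documents do not support that. The only age grouping they define is 3-5 / 6-8, and it may well be the one intended. Any power loss for age would depend on an age mix and a way of recording age that are not given, so no figure is offered.

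**Conclusion.** This is an efficiency improvement, not an error. A reader might infer that the split biases Aim 2 or inflates false positives; simulated rejection with no interaction is about 5% for both analyses, so that reading fails.

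For the 8 prior-distress models, if moderation is roughly linear and the score near normal, the split keeps about 64% of the information. At N=156 and an assumed 0.45 outcome SD per moderator SD, power is about 78% continuous against 55% split. The direction is firm under linearity. The size is illustrative, because alpha, effect size and distribution are assumed, and it is not a bound: the gain may be nil or negative if the true effect is a step or a plateau. The age point is a request for one clarifying sentence.

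**What to change.** In Section 7.0, replace the parenthesis on the median, for the two prior-distress moderators, with text such as:

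> The child and parent prior-distress scores at T1 (naming the instrument and score used for each) enter as continuous, mean-centred variables with a main effect and a product with arm. The product term is the primary moderation test. The median-split interaction is reported as a sensitivity result. The Aim 3 moderation models follow the same rule. The child-age interaction uses the 3-5 / 6-8 randomisation stratum.

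Naming the instruments is needed because the Section 6.0 table lists both under one heading without saying which supplies the child score and which the parent score.

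The cost is a few sentences and no new data. The downside is lower power for the primary test if the true effect is a step at the median (about 60% against 79%), and no gain or some loss under a plateau. Reporting the split alongside would let a reader see this, provided that it does not replace the primary test after the results are known.
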